9.3 POPULATIONS FOR ANALYSES

The following analysis populations will be considered:

- The safety population consists of all patients randomized in the study for whom there is any evidence that they used study medication and for whom any follow-up information is available.
- The Full Analysis Set (FAS) population consists of randomized study participants, potentially excluding a few participants who failed to take at least one dose of trial medication and had a very early withdrawal (first week after randomization) definitely not related to study medication and lacked any post randomization data (CPMP/ICH/363/96).
- The Per Protocol (PP) population will exclude FAS patients with major protocol deviations that are related to drug administration (e.g. a long interruption period, see section 7.1) that may impact the efficacy analysis. The exclusion of patients from the PP population will be determined in a blinded data review meeting that will be held prior to the disclosure of the randomization list. Reason(s) for exclusion will be provided for each patient.

The safety population (all the included patients having taken the product at least once) will be the set for the safety analyses.

Concerning the main endpoint and the key secondary endpoints, the FAS population will be the population of interest (main population). However, for sensitivity purpose, the corresponding analyses (mixed models and logistic regression models) will also be fitted on the PP population.

9.4 STATISTICAL ANALYSES

9.4.1 GENERAL APPROACH

The SAP will be finalized & signed-off before database lock and unblinding.

All inferential tests will be two-tailed and with a 5% alpha risk, unless otherwise specified.

Descriptive statistics (mean, standard deviation, 95% confidence interval for mean, minimum, median, maximum, and number of observations and missing cases) will be used for quantitative variables, and frequencies and percentages will be used for categorical variables. The descriptions will be broken down by treatment group.

A Hochberg procedure will be used to deal with the multiplicity concern on the main endpoint and the key secondary endpoints. Other multiplicity concerns (relative to secondary endpoints) are kept under control by the pre-specification of key-secondary endpoints and a low number of secondary endpoints and analyses.

Due to the quantitative form of the endpoints (gait speed PF10 and handgrip strength test) and the large number of patients, the normal assumption for the residuals of the mixed models will be assumed. However, if found necessary, additional non-parametric approach could be added and detailed in the SAP of the study.

The covariates included in the models are the stratification factors (gender and center) and the baseline score of the parameter if available. No interactions will be included by default in the models, however, in case of interesting findings in the subgroup analyses, further analyses would be conducted.

9.4.2 ANALYSIS OF THE PRIMARY EFFICACY ENDPOINT(S)

A Mixed Effect Model Repeat Measurement (MMRM) model with fixed factors in treatment, in centers, the baseline score and the stratification factor (gender) will produce an estimate of the contrast at M6 in the change from baseline of the 400MW test gait speed between each active arm and the placebo group (after adjustment by the Hochberg procedure).

The MMRM model will give a correct estimation in presence of missing data, under the Missing at Random (MAR) assumption. This analysis will provide an estimand of the efficacy of the tested product in the population that stayed in the study for the entire 6 months. Additional sensitivity analyses may be added in the SAP during the blind-review meeting if the number of missing data is important (more than 10%).

The same model will be also fitted in the Per Protocol population to give an estimand of the efficacy of the product in the population with good compliance.

Alternative methods to adjudicate missing data for the primary endpoint like the Bayesian Multiple Imputation (MI) methods could be considered and adopted before to finalize the SAP. Chen at al (2017) demonstrated the interest of applying Bayesian MI method to 400MW non-completers in the LIFE study⁶³.

Additionally, a responder analysis will be provided, using a logistic regression (with the same fixed factors as the mixed model) to model the chance to be a responder for the 400MW test (improvement of 0.1 m/s or more). The odds ratio of each active group versus placebo will be provided with a 95% confidence interval (CI).

9.4.3 ANALYSIS OF THE SECONDARY ENDPOINT(S)

The key secondary endpoints (handgrip strength and PF-10 sub-score of the SF-36) will be analyzed with the same strategy as the primary endpoint (i.e. using a repeated measures mixed model to estimate the contrast at M6 of the difference of each active group versus placebo).

Missing data will not be replaced in these analyses but the MMRM model on observed data is known to perform well under a MAR hypothesis.

Additional sensitivity analyses may be added in the SAP during the blind-review meeting if the number of missing data is important (more than 10%).

Concerning the responder endpoints:

- 1. for the PF-10 sub-score of the SF-36, a responder analysis will be performed with a responder definition of "patient with an improvement of PF-10 greater or equal to 2 points versus baseline", at an individual level.
- 2. for the handgrip strength test: a responder definition is equal to the minimal significant benefit set at least 2 kg of improvement versus baseline, at an individual level.

The rate of responders (according to the predefined definitions provided in the corresponding endpoint sections) will be provided in each group of treatment at M3 and M6 visits for the PF-10 sub-score and at the M6 visit only for the handgrip strength test. Participants without any assessment for a parameter at a visit will be considered as non-responder for the corresponding parameter.

A logistic regression model with treatment group, gender and center as fixed effects will be used to compare each active group versus placebo at M6. The odds-ratio comparing groups will be provided as well as its 95% confidence interval. The multiplicity issue due to the two doses of active treatment will be addressed using the Hochberg procedure.

The other secondary and exploratory endpoints will be analyzed only in the FAS population.

Details and exploratory endpoints analyses will be provided in the SAP.

9.4.4 IMPACT OF THE COVID-19 OUTBREAK

Due to the COVID-19 outbreak, an updated strategy for the final analysis will be implemented, to account for the missing data on safety and efficacy which will have impact on the final analysis This will include sensitivity analyses comprising before/during/after COVID_19 outbreak. This will be detailed in an updated version of the SAP.

In addition, sample-size reassessment, will take place, based on an interim analysis, which will take place once the COVID-19 restriction is lifted, to account for additional non-evaluable withdrawals and other considerations, based on reduced activity of participants due to restrictions.

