9.2 SAMPLE SIZE DETERMINATION

Originally, the sample size was calculated for a comparison test at a 0.05 two-sided significance level, a power of 80%, to detect a difference of 0.05 m/s (minimal clinically important difference) between active groups and placebo on the change from baseline in the 400 m gait speed at 6 months, with a standard deviation of 0.13 (estimated from the VIVE2 trial, Fielding et al, 2017⁶²).

After analysis of the preliminary data from our observational trial data (SARA-OBS, with approx. 105 completers), the following were learned:

- During the 6 months follow-up, this study population deteriorated as suggested by a decreased gait speed of 0.05 meter per second on the 400MW test, with a standard deviation of the change from baseline of 0.2
- The expected effect of BIO101 remains at 0.05 meter per second, as the change from baseline
- Together, this new information allows an increase of up to 0.1 m/s to be considered as a minimal clinically important difference of changes at the M6 visit from baseline between the treatment groups. Under these assumptions, a number of 64 patients/group is needed, giving a new sample-size of 192 patients for 3 arms, with a standard deviation of 0.20 (estimated from SARA-OBS preliminary data).

Taking into consideration this increased expected difference between treatment arms, a formal interim analysis will be performed by the DSMB when half subjects reach their month 6 visit (See section 9.4.6). Once half study participants complete their End-of intervention study visit, an unblinded 'promising zone' interim analysis will take place and determine if there is a need to increase the sample size based on the complete efficacy data.

Based on current calculation and given a limited 20% provision for premature withdrawals or lost-to-follow up, a total number of 231 participants will be included in the study.

It is expected, that due to COVID-19 related restrictions, that the number of non-evaluable withdrawals will be higher than 20%. However, reassessment of the sample size, will take place, as a part of the interim analysis, that will take place after restrictions are lifted.

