9.4.7 PLANNED INTERIM ANALYSIS

The primary endpoint is the gait speed measured during the 400MW test. The group-sequential design consists in one interim analysis, which was originally planned to take place when 50 participants have finished their participation. Due to the COVID-19 restrictions, this analysis is postponed. The timing of this analysis will be defined once restrictions are lifted and will take into account, COVID-19 related non-evaluable withdrawals and reduction of activity.

The sample size increase will use the 'promising -zone' method of Mehta and Pocock (Mehta, 2011)⁶⁴ for an interim analysis. This approach ensures that the sample size is only increased in case the interim results are promising, in which case the overall type-I error is not inflated by use of the conventional Wald statistic. More specifically, this 'promising zone' is defined in terms of the conditional probability of rejecting the null-hypothesis at final analysis, given the estimated difference at interim ('conditional power') and assuming that this estimated difference is the true underlying difference. Depending on the conditional power (CP) at interim analysis, we consider three different zones and anticipated actions:

1. Unfavorable zone

The interim results are so disappointing that it is not worth to increase the sample size to retrieve CP and the original sample size is retained. This zone will be defined for a sample size reassessment at 50% information fraction and a maximal increase in sample size 100 additional

participants. Note that in case the observed gait speed difference at interim below the threshold defined in the SAP, the study would stop for futility.

2. Promising zone:

If the CP is below the originally planned 0.80, the sample size will be increased to the maximal sample size of 330.

3. Favorable zone

The conditional power is at least 0.80. In this zone, the interim results are sufficiently favorable for the trial to continue to the original sample size without the need to adaptively increase the trial size.

The DSMB will be responsible for reviewing accumulated safety and efficacy data at intervals throughout the study.

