5 SAMPLE SIZE AND POWER

Originally, the sample size was calculated for a comparison test at a 0.05 two-sided significance level, a power of 80%, to detect a difference of 0.05 meters per second (minimal clinically important difference) between active groups and placebo on the change from baseline in the 400 m gait speed at 6 months, with a standard deviation (SD) of 0.13 (estimated from the VIVE2 trial, Fielding et al, 2017^3).

Based on current calculation and given a limited 20% provision for premature withdrawals or lost-to-follow up, a total number of 231 participants will be included in the study.

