8.10 Interim analysis

Not Applicable.

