8.11 Data Safety Monitoring Board

The DSMB will be responsible for reviewing accumulated safety and efficacy data at intervals throughout the study.

The DSMB is periodically reviewing all safety data and raise alerts in case of negative or dangerous findings. Members of the DSMB will be selected based on their expertise by the SARA managing Board.

During the COVID-19 outbreak, the DSMB is meeting at least every other week to review its recommendation based on update of guidance from the national health agencies and local status.

Version Final 2.0, Date: 04JUN2021

In particular, the DSMB will evaluate the results of a formal pre-planned interim futility analysis and sample size reassessment. The DSMB will recommend to the Sponsor whether to continue, modify or stop the clinical trial based on futility but also on safety issues or other considerations not related to efficacy or safety. In case the study continues and the original sample size is retained, the DSMB will not communicate to anyone whether this is due to unfavorable or favorable results.

CHANGES TO PLANNED ANALYSIS FROM STUDY PROTOCOL

- The text from the protocol ''and for whom any follow-up information is available'' is not included in the definition of the safety population, thus more closely aligned with the definition in CPMP/ICH/363/96.
- The protocol mentioned '' The study would stop for futility at the interim analysis if a gait speed difference below the threshold defined in the SAP is observed." The interim analysis (IA) will no longer include the possibility of stopping for futility as all patients will have been recruited before the IA occurs. The details of the IA will be contained in the IA SAP.
- 'Month 6' is updated to 'Month 6/Month 9' in SAP due to COVID-19 except for section '5 SAMPLE SIZE AND POWER'
- 'Additional sensitivity analyses may be added in the SAP during the blind-review meeting if the number of missing data is important (more than 10%).' is removed from SAP, and section '8.7.6.1 Sensitivity Analyses of Missing data by Using Bayesian Multiple Imputation (MI) Methods' is added due to COVID-19.
- Additional analysis for primary endpoint is planned. Last assessment on treatment will be derived and analyzed.

9

10 **REFERENCES**

- 1. ICH Topic E3: Structure and Content of Clinical Study Reports (CPMP/ICH/137/95adopted December 1995).
- ICH Topic E9: Statistical Principles for Clinical Trials (CPMP/ICH/363/96 adopted March 1998).

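### The interim reassessment is said to cover losses above 20%, but its written rule responds only to conditional power, so 64 evaluable per group is not assured

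*Protocol*

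**What the plan says.** **Expected loss.** Protocol 9.2 asks for 64 per group (192 in total), allows 20% for losses and arrives at 231. It then says it is expected "that the number of non-evaluable withdrawals will be higher than 20"%, because of COVID-19 restrictions, and turns to a reassessment at the interim. Protocol section 5 says the same.

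**Purpose given to the reassessment.** Protocol 9.4.4 places it "once the COVID-19 restriction is lifted, to account for additional non-evaluable withdrawals and other considerations".

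**The rule.** Protocol 9.4.7 has three zones, defined by conditional power (CP).
- Unfavorable: the original size is kept.
- Promising, with CP below 0.80: the size goes to 330.
- Favorable, with CP at least 0.80: "the interim results are sufficiently favorable for the trial to continue to the original sample size".

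COVID-19 withdrawals appear in that section only as something to consider when choosing the date of the interim.

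**The SAP.** Section 5 sets 231 "given a limited 20% provision for premature withdrawals or lost-to-follow up" and does not mention the higher expected loss. Section 8.10, on the interim analysis, reads "Not Applicable". Section 8.11 nevertheless has the DSMB evaluate a planned interim and a sample-size reassessment. The changes section removes the futility stop because "all patients will have been recruited before the IA occurs", and sends the details of the interim to a separate interim SAP.

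**The concern.** The protocol identifies a threat to its sample size and names a remedy, but the remedy as written is driven by something else. A promising-zone rule adds participants when the interim effect is encouraging but short of the target. It is not built to replace missing participants. A trial with 35% loss and a strong interim effect keeps 231, and so does one with 35% loss and a weak effect.

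The SAP is dated more than a year after the protocol version that expected the higher loss, yet it carries the 20% figure unchanged. The two documents thus hold different loss assumptions, and the step meant to join them does not use the loss.

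What is at stake is how the result is read. A null finding would be judged against 64 evaluable per group and 80% power, when the plan itself expected to fall below that.

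**Working it through.** **Inputs**
- Difference 0.10 m/s: Protocol 9.2, where "this new information allows an increase of up to 0.1 m/s to be considered as a minimal clinically important difference".
- SD 0.20, 64 per group, 192 in total, 231 randomised: Protocol 9.2. Allocation 1:1:1: Protocol 4.1.
- Alpha and power: Protocol 9.2 states a "comparison test at a 0.05 two-sided significance level, a power of 80"% for the original calculation only. I assume both carry over.
- Loss rate: above 20%, no figure given. I use 20% to 40% as an assumed range.

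**Reproducing 64 per group.** Normal approximation: n = 2 × [0.20 × (1.960 + 0.842) / 0.10]² = 62.8, so 63. By the two-sample t-test, with noncentrality (0.10/0.20) × √(n/2) and 2n − 2 degrees of freedom, power is 79.5% at 63 and 80.1% at 64. The 64 is reproduced.

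**Reproducing 231.** 192 × 1.2 = 230.4, so 231. Dividing by the retained fraction gives 192/0.8 = 240. The loss at which 231 still yields 64 per group is 1 − 192/231 = 16.9%, so 231 falls slightly short even at the planned 20%.

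**Power if 231 is kept.** Evaluable n per group = 231 × (1 − loss)/3, with power by the same t-test. The 240 column separates out the effect of the 20% inflation method.

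| Loss | n per group (231) | Power (231) | Power (240) |
|---|---|---|---|
| 20% | 61.6 | 78.6% | 80.1% |
| 25% | 57.8 | 75.9% | 77.5% |
| 30% | 53.9 | 73.0% | 74.6% |
| 40% | 46.2 | 66.2% | 67.9% |

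Against 80.1%, the gap at 231 is about 4 points at 25% loss, 7 at 30% and 14 at 40%. About 1.6 points of each come from 231 rather than 240. The rest, about 2.6, 5.5 and 12 points, comes from loss above 20%.

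**The same result as a detectable difference.** At 80% power this scales as 0.10 × √(64/n): 0.105 m/s at 25% loss, 0.109 at 30% and 0.118 at 40%.

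**Size needed to keep 192 evaluable.** 192/(1 − loss): 256 at 25%, 275 at 30%, 320 at 40%.

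**If the promising zone is reached.** 330 × 0.70/3 = 77.0 per group at 30% loss (power 86.9%), and 330 × 0.60/3 = 66.0 at 40% (81.4%). It holds 64 per group up to a loss of 1 − 192/330 = 41.8%.

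**How often the favorable zone would apply (illustration).** Assume one comparison, half the information, CP on the current trend and a true difference of 0.10. Then CP = Φ[(z₁/√0.5 − 1.96)/√0.5], which reaches 0.80 at z₁ = 1.81. The chance of that is about 58% if 64 per group are evaluable at the end and 51% if 53.9 are. In those trials no participants are added, whatever the loss.

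**The case against.** **The SAP keeps an interim.** A reader of SAP 8.10 alone might infer that it has been abandoned. The documents do not support that. The SAP is written for the final analysis, so 8.10 may be a statement of scope. Section 8.11 and the changes section keep an interim and a reassessment, and a loss-based rule could sit in the unseen interim SAP. This stands. What remains is that the SAP's sections conflict and none states a rule.

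**64 per group may still be reached.** A reader might conclude that it will not be. The increase to 330 would secure it up to 41.8% loss, so that conclusion is too strong. The trigger, however, is the interim effect.

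**Most trials would keep 231.** One might put this at about 80%, but that needs a lower CP bound of 0.36 to 0.41, which the documents do not give. With a bound of 0.10 the share is 65% to 68%. No single figure can be defended.

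**Other measures recover information.** Treatment can be extended so that a missed Month 6 walk is made at Month 9, and SAP 8.7 uses M9 when M6 is missing. The MMRM also uses Month 3 data, and the synopsis allows randomisation to resume. The power figures give lost participants no weight, so they overstate the loss of power to some degree. But the protocol version that introduced the extension still expected more than 20% loss, and the resumption has no number or rule.

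**CP may depend on loss indirectly.** If CP were computed on the projected evaluable number, higher loss would lower it. Protocol 9.4.7 does not say which number is used.

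**The reader is warned and the counts are reported.** The protocol states the higher expected loss openly. The SAP reports numbers analysed by arm with confidence intervals (8.7.1.1) and numbers completing each visit (8.3). This limits the harm but does not correct the purpose given in 9.4.4 or the figure in SAP section 5.

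**Conclusion.** The point holds as an inconsistency with a moderate consequence. Protocol 5, 9.2 and 9.4.4 credit the reassessment with a property that the rule in 9.4.7 lacks, and SAP section 5 keeps a loss assumption that the protocol no longer held. The 64 evaluable per group is not assured. That is as far as the documents go.

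If the size stays at 231, the effect is small near 20% to 25% loss and material at 30% to 40%, where power falls to between 73% and 66%. These figures assume one dose against placebo at an unadjusted two-sided 0.05, a difference of 0.10 m/s, SD 0.20, no information from lost participants, and a loss rate that the documents do not give.

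A loss-based rule in the interim SAP would answer much of the concern about the mechanism. Protocol 9.4.7 and SAP section 5 would still need to agree with Protocol 9.4.4.

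**What to change.** 1. In Protocol 5, 9.2 and 9.4.4, state that the promising-zone reassessment responds to conditional power and does not by itself make good non-evaluable withdrawals.
2. Reconcile SAP 8.10 with 8.11 and the changes section, so that the SAP says once whether an interim and a reassessment take place and which document holds the rule.
3. In SAP section 5, replace the sentence giving 20% and 231 with the power for 0.10 m/s at SD 0.20, or the detectable difference, at the number evaluable for the M6/M9 walk. Take that number from a blinded count, and show the range above until it is known.

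The cost is wording in both documents and one blinded count, with no extra participants and no unblinding. The change does not restore the lost participants. It makes the stated power match the trial, and that power will be less favourable.

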9.4.5 SAFETY ANALYSES

Safety variables will be summarized/analyzed by groups of treatment, on the Safety population.

Vital signs, biochemistry and hematology parameters will be described by descriptive statistics, for the entire period of the study and at each timepoint.

Usual tables (by SOC and preferred term) will be produced for AEs (falls, injurious falls and orthostatic hypotension will be tabulated separately) after coding with the MEDRA terms.

9.4.6 BASELINE DESCRIPTIVE STATISTICS

The disposition of study participants at each visit will be described, by treatment groups and overall, as well as the number of premature discontinuations and their main reasons.

Demographic and baseline characteristics of the patients will be presented overall and by treatment arms with descriptive statistics (mean, standard deviation, median, range and number of missing cases for quantitative parameters and percentages and number of missing cases for the qualitative parameters).

Compliance will also be described and compared by treatment groups. Details of the calculations will be provided in the SAP of the study.

